6.3.13.2 Statistical Methods for Primary Immunogenicity Analyses

Geometric mean concentration (GMC) of anti-HBsAg antibody ratios 4 weeks after the third injection

All statistical analyses will be performed on the logarithmically (base 10) transformed values.

Adjusted estimates of GMCs and their associated 95% CIs will each be determined using an analysis of covariance (ANCOVA) model with a factor for vaccine lot group, and a covariate for the log transformed pre-vaccination (baseline) titer. Data from all centers will be pooled. For each vaccine lot, antibody GMCs, associated standard errors, two-sided 95% CIs and median, minimum, and maximum titer values will be determined and presented by lot group. The median, minimum, and maximum values will be reported on the actual titer values, rather than the log scale. The ratio in GMCs between each vaccine lot group (GMC(group A)/GMC(group B), GMC(group A)/GMC(group C), GMC(group B)/GMC(group C)), and their associated two-sided 95% CIs will also be presented.

PAREXEL International

Statistical Analysis Plan

Sensitivity analyses using the same modeling approach outlined above will be conducted using the FAS. These analyses will be reported both with and without patients in the FAS who are seropositive at baseline.

If this condition is satisfied with either PPS1 or PPS2, then manufacturing equivalence (lot-to-lot consistency) will be demonstrated.

Sample SAS code for assessment of lot-to-lot equivalence:

- Sample SAS code for ANCOVA model:

```
PROC MIXED;  
CLASS treatment;  
MODEL log (var) = treatment log (baseline of var);  
LSMEANS treatment / DIFF CL ALPHA=0.05;  
ODS OUTPUT LSMEANS=ls_means Diffs=diff;  
QUIT;
```

where var represent the anti-HBs titer and treatment represents vaccine lot group.

6.3.13.3 *Secondary Objective Analyses*

If lot-to-lot consistency is demonstrated, then the data from the three lots will be combined to address the secondary immunogenicity non inferiority-hypothesis. It is to demonstrate that the SPR 4 weeks after completion of the three-dose regimen of Sci-B-Vac™ is non-inferior to the SPR 4 weeks after completion of a three-dose regimen of Engerix-B®. Seroprotection is defined as anti-HBs levels ≥ 10 mIU/mL in serum. Seroprotection rate (SPR) is the percentage (%) of subjects achieving seroprotection.

Seroprotection rate (SPR) 4 weeks after the third injection

Non-Inferiority of Sci-B-Vac™ 4 weeks following the third vaccination compared to Engerix-B® 4 weeks following the third vaccination will be assessed using PPS2. Data from all centers will be pooled and data from all 3 lots of Sci-B-Vac™ will be pooled. The difference in proportions [SPR(Sci-B-Vac™) – SPR(Engerix-B®)] and two-sided 95% CIs, will be calculated using the Miettinen and Nurminen method. Funnel plot will be produced to investigate the impact of center.

Sample SAS code for assessment of non-inferiority:

- Sample SAS code for the analysis of binary data:

```
PROC FREQ; * specify and sub-select data set as applicable;  
TABLES trt*seroprotection/riskdiff (cl=mn); * numerical 0/1-scores identify 'event';  
RUN;
```

PAREXEL International

Statistical Analysis Plan

where seroprotection represent the seropositive event and trt represents treatment group.

If the lower bound of the 95% Miettinen-Nurminen CI is greater than -5%, Sci-B-Vac™ will be declared non-inferior to Engerix-B®.

Sensitivity analyses using the same modeling approach outlined above will be conducted using the FAS and ITT. For these ITT analyses, patients with missing data at Day 196 (4 weeks following the third vaccination) will be included and treated as failures. These analyses will be reported both with and without patients who are seropositive at baseline.

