3. STUDY POPULATION

Per protocol, the study population will consist of approximately 3200 adult subjects (18-45 years) in at least 30 study centers in the E.U., Canada and the U.S. of all races and ethnic groups meeting all the inclusion criteria and none of the exclusion criteria. The final study population consisted of approximately 2800 adult subjects after an early closure to enrollment (see [Section 4](#)).

Inclusion criteria

Subjects must meet all the following criteria:

1. Any gender.
2. Age 18-45 years.
3. Healthy, as determined by a physical examination and values of laboratory tests.
4. If female: a) either not of childbearing potential, defined as postmenopausal for at least 1 year or surgically sterile (bilateral tubal ligation, bilateral oophorectomy or hysterectomy), OR b) is of childbearing potential and must agree to use an adequate birth control method during the screening period and until the end of her participation in the study (effective birth control includes: 1) hormonal

PAREXEL International Statistical Analysis Plan

(implant, oral, vaginal, transdermal) contraceptives; 2) diaphragm with spermicide, condom (with or without spermicide); 3) intra-uterine devices; and 4) vasectomy of male partner; 5) abstinence from penile-vaginal intercourse (if the preferred and usual lifestyle of the subject)).

5. Able and willing to give informed consent.

Main Exclusion criteria

Main exclusion criteria are listed below, for the complete list of exclusion criteria please refer to [section 4.1.2 of the Protocol](#). Participants meeting any of the exclusion criteria will be excluded.

1. Previous vaccination with any HBV vaccine (licensed or experimental).
2. Treatment by immunosuppressant within 30 days of enrollment including but not limited to corticosteroids at a dose that is higher than an oral or injected physiological dose, or > 20 mg /day prednisolone equivalent (Inhaled and topical steroids are allowed).
3. History of immunological function impairment, including but not limited to:

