4. STATISTICAL BASIS FOR SAMPLE SIZE

The sample size for this study is driven by the lot-to-lot consistency requirement. A total of 800 subjects in each of the three Sci-B-Vac™ lots will provide at least 90% power to ensure that the 95% confidence interval for each pairwise difference (GMC of anti-HBs in group A/GMC of anti-HBs in group B, GMC of anti-HBs in group A/ GMC of anti-HBs in group C, GMC of anti-HBs in group B/ GMC of anti-HBs

PAREXEL International Statistical Analysis Plan

in group C) in normalized log₁₀ (GMC) will have a lower bound that is >-0.176 and an upper bound that is <0.176 if the true standard deviation is ≤ 0.9 ; this corresponds to the true GMC ratio falling between $2/3$ and $3/2$. With an active comparator arm of Engerix-B[®] of equal size ($n=800$), the total sample size of the study is 3,200.

If lot-to-lot consistency is demonstrated, all three Sci-B-Vac[™] lots will be pooled together to test that the Seroprotection Rate (SPR) four weeks after completion of the three-dose regimen of Sci-B-Vac[™] is non-inferior to a three-dose regimen of Engerix-B[®]. Assuming 10% of the subjects are non-evaluable (i.e., 2880 are evaluable, with 2160 randomized to Sci-B-Vac[™] and 720 to Engerix-B[®]), a two-sided 5% significance level and a non-inferiority margin of -5% , the non-inferiority test will have $> 90\%$ power. The following table provides the estimated power under different assumptions of the SPR four weeks after completion of the three-dose regimens.

Response in Engerix-B [®] (N=720)	Response in Sci-B-Vac [™] (N=2160)	Power
80%	85%	99%
85%	85%	92%
90%	95%	99%

In October 2018, enrollment was closed early for non-safety-related reasons after 2838 were randomized to the study. With approximately 700 subjects in each of the three Sci-B-Vac[™] lots and 700 subjects in comparator arm of Engerix-B[®], the sample size will provide $> 80\%$ power to evaluate both the primary objective of lot to lot consistency of the three Sci-B-Vac lots, and the secondary objective of non-inferiority of Sci-B-Vac[™] vs Engerix-B[®].

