5. RANDOMIZATION

A statistician who is not involved in the clinical aspects of the study will generate a permuted blocked randomization list for each site. Randomization will be via a web-based IWRS, stratified by study center. The site pharmacy and/or unblinded study center staff will receive a notification of the randomization, which should be filed in a locked area/ computer folder not accessed by blinded study center staff.

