6.2.7 Sub Groups

The following key sub-groups of interest will be pre-specified:

- Gender (male vs female)
- BMI (≤ 30 vs > 30)
- Smoking Status (current vs past or non-smoker)
- Daily alcohol consumption (≥ 4 drinks/day vs 2-3 drinks/day vs 0-1 drink/day)
- Non-study licensed vaccine (no vaccination vs vaccination)
- Race (White vs Black or African American vs Other)
- Ethnicity (Hispanic or Latino vs Non Hispanic or Latino)
- Country/region (United States vs Canada vs Europe)

PAREXEL International
Statistical Analysis Plan

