6.3.13.4 Exploratory Objective Analyses

Analysis of all exploratory immunogenicity endpoints will be based on PPS2, unless otherwise indicated. Exploratory efficacy endpoints will be summarized and analyzed without adjustment for multiple comparisons.

Each of the exploratory endpoints defined in the protocol will be summarized for each Sci-B-Vac™ lot separately, as well as for the difference between each Sci-B-Vac™ lot. Analysis of GMC endpoints will use the same methods as described above for the primary endpoint. For binary data, proportions and two-sided 95% CIs will be reported. The difference in proportions and two-sided 95% CIs, will be calculated using the Miettinen and Nurminen method.

In addition, each of the exploratory endpoints will be summarized with data from all 3 lots of Sci-B-Vac™ pooled together. Summaries will be presented for Sci-B-Vac™, Engerix-B™ and for the treatment difference. Adjusted estimates of GMCs and their associated 95% CIs will each be determined using an analysis of covariance (ANCOVA) model with a factor for treatment group, and a covariate for the log transformed pre-vaccination (baseline) titer. For each treatment group, anti-HBs GMCs, associated standard errors, two-sided 95% CIs and median, minimum, and maximum titer values will be determined and presented by treatment group. The median, minimum, and maximum values will be reported on the actual titer values, rather than the log scale. The ratio in GMCs between treatment groups (GMC of anti-HBs in Sci-B-Vac™ / GMC of anti-HBs in Engerix-B®), and their associated two-sided 95% CIs will also be presented. For binary data, proportions and two-sided 95% CIs will be reported. The difference in proportions and two-sided 95% CIs, will be calculated using the Miettinen and Nurminen method.

Please see [Section 6.3.13.2](#) and [Section 6.3.13.3](#) for sample codes. Per sponsor's request, one additional pre-specified exploratory analysis has been added to the SAP. This additional exploratory analysis is as follows:

PAREXEL International
Statistical Analysis Plan

- To determine whether the SPR after 2 vaccinations with Sci-B-Vac™, evaluated 20 weeks after the second vaccination (just prior to receiving the third vaccination), is non-inferior to the SPR 4 weeks after receiving the third vaccination with Engerix-B®.

This additional exploratory analysis will be summarized with data from all 3-lots of Sci-B-Vac™ pooled together.

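### Lots are randomized within study center, but the primary lot-consistency ANCOVA leaves center out, so its confidence intervals are wider than necessary if center explains variance in anti-HBs

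*SAP*

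**What the plan says.** On allocation, SAP section 5 provides for a separate permuted-block list at each site and states: "Randomization will be via a web-based IWRS, stratified by study center". Section 3 plans to recruit "in at least 30 study centers in the E.U., Canada and the U.S".

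On analysis, section 6.3.13.2 specifies an ANCOVA of log10 anti-HBs "with a factor for vaccine lot group, and a covariate for the log transformed pre-vaccination (baseline) titer. Data from all centers will be pooled". The sample PROC MIXED code agrees: its model line is "MODEL log (var) = treatment log (baseline of var"), treatment is the only CLASS variable, and there is no RANDOM statement. The FAS sensitivity analyses reuse this model. Section 6.3.13.4 extends it to the exploratory lot comparisons: "Analysis of GMC endpoints will use the same methods as described above for the primary endpoint".

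The only planned look at center is a funnel plot, placed under the secondary seroprotection analysis in section 6.3.13.3. No analysis of the lot ratios adjusts for center, and no reason is given for leaving it out.

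**The concern.** Stratified blocks give each center nearly equal numbers on each lot, so a high-responding or low-responding center shifts all three lot means by about the same amount. The lot differences therefore carry almost no between-center variation. A model without center still counts that variation as residual error, so its standard error overstates the true sampling error of the lot differences.

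The cost is power. All three pairwise intervals must lie inside the margin, and the lots are pooled for the secondary non-inferiority test only if they do. A chance failure on lots therefore also closes the planned route to the secondary claim. There is little slack, because "enrollment was closed early for non-safety-related reasons after 2838 were randomized to the study", against a planned 3,200.

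**Working it through.** **Inputs from the SAP.** Margin ±0.176 on log10, two-sided 95% intervals and three pairwise comparisons (sections 4 and 6.3.13.1). Section 4 requires "an upper bound that is <0.176 if the true standard deviation is" at most 0.9. It gives 800 per lot as planned and about 700 after early closure (2,838/4 ≈ 709). It also gives 10% non-evaluable, stated there for the secondary test; 700 × 0.9 = 630.

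**Assumptions.** The SAP gives no ICC, so 0, 0.02, 0.05 and 0.10 are used. It gives only an upper bound for the SD, so 0.8 and 0.7 are shown beside 0.9. The true lots are taken as equal, and the baseline covariate is left out.

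**The plan's own figure.** Power per pair = 2Φ(0.176/(SD√(2/n)) − 1.96) − 1. For n = 800 and SD 0.9, 0.176/0.045 = 3.911 and 2Φ(1.951) − 1 = 94.9%. This agrees with the stated minimum of 90% for each pairwise comparison, and that statement is not disputed. For all three pairs together, power at ICC 0 is 87.6% with 800 per lot, 80.3% with 709, 79.4% with 700 and 71.4% with 630.

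**Effect of center.**
- True SE of a lot mean under center blocking ≈ SD√(1−ICC)/√n.
- Half-width without center = 1.96·SD·√(2/n).
- Half-width with center = 1.96·SD·√(1−ICC)·√(2/n).
- Joint power = P(range of three lot means < 0.176 − half-width), from the studentized range distribution.

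Example with n = 700, SD 0.9 and ICC 0.10:
- SE = 0.9 × 0.9487/26.46 = 0.0323.
- Without center: half-width 0.0943, (0.176 − 0.0943)/0.0323 ≈ 2.53, power 82.7%.
- With center: half-width 0.0894, (0.176 − 0.0894)/0.0323 ≈ 2.68, power 86.0%.

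Joint power at SD 0.9, without → with center:

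| ICC | Width ratio | 700 per lot | 630 per lot |
|---|---|---|---|
| 0 | 1.000 | 79.4% → 79.4% | 71.4% → 71.4% |
| 0.02 | 1.010 | 80.1% → 80.8% | 72.1% → 73.1% |
| 0.05 | 1.026 | 81.1% → 82.8% | 73.2% → 75.5% |
| 0.10 | 1.054 | 82.7% → 86.0% | 75.1% → 79.4% |

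Gain in percentage points for ICC 0.02 / 0.05 / 0.10, from unrounded powers:

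| SD | 700 per lot | 630 per lot |
|---|---|---|
| 0.9 | 0.7 / 1.8 / 3.3 | 0.9 / 2.2 / 4.3 |
| 0.8 | 0.3 / 0.8 / 1.4 | 0.5 / 1.2 / 2.2 |
| 0.7 | 0.1 / 0.2 / 0.3 | 0.2 / 0.4 / 0.6 |

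At 709 per lot and SD 0.9 the gains are 0.7 / 1.7 / 3.2.

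**Direction of the error.** Coverage of the nominal 95% interval without center = 2Φ(1.96/√(1−ICC)) − 1 = 95.2%, 95.6% and 96.1% for ICC 0.02, 0.05 and 0.10. The interval is conservative.

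**Simulation check.** 3,000 runs per case; 2,838 randomized 1:1:1:1; centers of unequal size; block size 8 (assumed); 10% excluded at random, leaving about 640 per lot; centers with fewer than 12 subjects combined into three regions. Joint power at SD 0.9, without → with center:

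| ICC | 30 centers | 60 centers |
|---|---|---|
| 0 | 72.9% → 73.0% | 72.0% → 71.4% |
| 0.02 | 72.7% → 73.8% | not run |
| 0.05 | 74.2% → 76.6% | 75.1% → 77.2% |
| 0.10 | 76.3% → 81.0% | 74.8% → 79.4% |

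The Monte Carlo standard error of each power is at most about 0.8 points, and both models were fitted to the same data sets. The simulation agrees with the closed form. When center explains nothing, including it changes power by +0.1 to −0.6 points.

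**The case against.** The strongest reply is that pooling over centers is an explicit choice. Text and code agree, the test is valid and prespecified, and nothing in the SAP contradicts it. The trial was also sized on a total SD of up to 0.9 with no credit for center. At the same SD and n, power without center rises with ICC, from 79.4% to 82.7% at 700 per lot, so the omission never takes power below the planning basis. What is lost is an available gain. All of this stands, and it is why the point concerns efficiency and not validity.

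The size is also unknown. The population is healthy, aged 18 to 45 and not previously vaccinated against HBV, and the per-protocol sets are seronegative at baseline. That may limit variation between centers, though the SAP cannot settle it. Seronegativity also probably leaves the one retained covariate little to explain.

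A third reply is that replacing the primary model brings in new choices, such as how to combine small centers, and that the protocol, not shown here, may fix the same model. A center-adjusted sensitivity analysis would then be the lighter request. This is fair as to cost, and the protocol would need checking. It does not remove the point: a sensitivity analysis would not narrow the intervals that decide the primary objective, and the new choices can be fixed before unblinding.

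**Conclusion.** The concern holds as a low-cost improvement, not as an error in the test. The design stratifies by center and the primary model ignores center. If center explains any variance in log10 anti-HBs, the lot-ratio intervals are wider than they need to be and joint power is lower than it could be.

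In closed form the loss runs from near 0 to about 4 points; the largest simulated difference is 81.0 − 76.3 = 4.7 points. The upper end needs SD 0.9, ICC 0.10 and about 10% exclusions together. At 700 per lot, SD 0.9 and ICC 0.10, a 3.3-point gain removes 3.3/17.3 = 19% of the failures of truly equal lots. At SD 0.7 the gain is at most 0.6 points.

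These figures cover one analysis set. Section 6.3.13.2 accepts success in either PPS1 or PPS2, which raises the chance of success under both models.

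**What to change.** Before unblinding, amend section 6.3.13.2 and its sample code:

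- Put study center in the CLASS statement and fit log10(anti-HBs) = lot + center + log10(baseline titer).
- Fix a rule for small centers. For example, combine centers with fewer than 12 evaluable Sci-B-Vac subjects within the section 6.2.7 categories, "Country/region (United States vs Canada vs Europe"). The threshold of 12 is a suggestion. Center as a random effect is an alternative that needs no combining.
- Keep the present model without center as a sensitivity analysis.
- Carry the change into the exploratory lot comparisons of GMC in section 6.3.13.4, which inherit the primary method.

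The cost is one model term, one CLASS variable and one combining rule. Center is already recorded for the randomization. With 30 centers the term uses about 29 degrees of freedom out of roughly 1,900 to 2,100 (3 × 630 = 1,890; 3 × 709 = 2,127). If the protocol specifies the same model, it needs a matching change.

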6.1.1 Derived and Computed Variables

Demographics

Body Mass Index (BMI, kg/m²) will be calculated using the following formula:

$$\text{BMI} = \text{Weight (kg)} / \text{Height}^2 (\text{m}^2)$$

Immunogenicity

Values below the lower limit of quantification (recorded as “< LQ”) will be set to half that limit (LQ/2).

Values above the upper limit of quantification (recorded as “>UQ”) will be set to that upper limit (UQ).

Titer greater or equal to a given threshold is defined as binary variable for non-missing values as:

= 1, if the titer is superior or equal to the given threshold

= 0, otherwise

Seroprotection is defined as binary variable for non-missing values as:

= 1, if anti-HBs levels \geq 10mIU/mL in serum

= 0, otherwise

Seroprotection rate (SPR) is the percentage (%) of subjects achieving seroprotection.

PAREXEL International

Statistical Analysis Plan

An initial result of ≥ 5.0 and < 12.0 mIU/mL (“Indeterminate”) required duplicate retest per Laboratory Procedure Manual. In the statistical analysis, if the anti-HBs serology result is initially indeterminate, then the average of initial and repeat samples will be calculated. Seroprotection will be determined as follows: if the average of initial and repeat samples is ≥ 10 mIU/mL, then it will be considered seroprotected. If it is less than 10 mIU/mL will be considered not seroprotected.

Geometric Mean Concentration

The GMC will be calculated using the following formula:

$$10^{\left\{ \frac{\sum_{i=1}^n \log_{10}(t_i)}{n} \right\}}$$

where t_1, t_2, \dots, t_n are n observed immunogenicity titers/concentrations.

Solicited Adverse Events

Reactions at the site of injection (redness/erythema, pain, tenderness, swelling/edema, pruritus), systemic reactions (nausea/vomiting, diarrhea, headache, fatigue, myalgia) and vital signs abnormalities (fever, tachycardia, bradycardia, hypertension, hypotension, changes in respiratory rate).

Unsolicited Adverse Events

All adverse events will be characterized according to the date of occurrence related to the vaccination phase as follows:

- **Emergence before vaccination phase:** start date before the first date of injection of study vaccine.
- **Emergence during vaccination phase:** start date on or after the first date of injection of study vaccine or, adverse event increase in severity including to “serious” adverse event.

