6.2.5 Per Protocol Sets

6.2.5.1 Per Protocol Set 1 (PPS1)

All subjects in the FAS who:

- received all 3 vaccinations
- have an evaluable serum immunogenicity samples at baseline and at the time point of interest
- are seronegative at baseline
- had no major protocol deviations leading to exclusion, which will be identified prior to unblinding.

A major protocol deviation for the purpose of exclusion from the PPS1 is defined as a protocol deviation that is considered to have a significant impact on the immunogenicity result of the subject.

These will be identified prior to unblinding and analysis and may include:

- subjects enrolled who did not meet study entry criteria
- subjects who did not receive the correct treatment
- subjects who developed withdrawal criteria but were not withdrawn
- subjects who received a prohibited concomitant medication

PAREXEL International Statistical Analysis Plan

- subjects with a deviation identified through monitoring visits or otherwise, where the deviation is judged to impact the reliability of subject immunogenicity results

PPS1 will be used for the primary endpoint analysis.

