6.2.5.2 Per Protocol Set 2 (PPS2)

All subjects in PPS1, but excluding those who attended study visits outside of the following windows:

- V3/Day 168 (+/- 28 days)
- V4/Day 196 (-7/+14 days)

PPS2 will be used for the primary, secondary, and exploratory endpoints.

In case of vaccination error, subjects in PPS1 and/or PPS2 will be analyzed “as randomized” and the subject who received the wrong vaccination will be excluded from PPS1 and/or PPS2. If a subject receives a vaccine from the wrong kit number, but the same as the one the subject was randomized to, the subject will not be removed from PPS1 and/or PPS2.

If a subject is unblinded during the study, except for suspected unexpected serious adverse reaction (SUSAR), he/she may be excluded from PPS1 and/or PPS2 based on sponsor’s decision with respect to any potential bias that may be introduced in the analysis of the primary and key secondary immunogenicity analyses.

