6.3.13.1 Primary Hypothesis

The lot-to-lot equivalence, in terms of immunogenicity, of three independent consecutive lots of the Sci-B-Vac™ will be demonstrated if the following condition is satisfied:

The upper and lower bound of the two sided 95% CI of the geometric mean concentration (GMC) of anti-HBsAg antibody ratios 4 weeks after the third injection for all three pairwise comparisons (GMC(group A)/GMC(group B), GMC(group A)/GMC(group C), GMC(group B)/GMC(group C)) are within [0.67, 1.5]

The analysis will use a two-sided 5% significance level. PPS1 and PPS2 will be used to test the primary hypothesis.

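### In the sets that decide lot consistency, the only ANCOVA covariate (log baseline titer) probably varies little or not at all, so precision available from other baseline data is forgone

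*SAP*

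**What the plan says.** **Model.** SAP section 6.3.13.2 obtains adjusted GMCs and their ratios from an ANCOVA on log10 titers with a factor for lot and "a covariate for the log transformed pre-vaccination (baseline) titer". The sample SAS code has the same two terms. Centers are pooled and nothing else enters.

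**Deciding sets.** Section 6.3.13.1 states that "PPS1 and PPS2 will be used to test the primary hypothesis". Subjects in PPS1 must be such that they "are seronegative at baseline" (section 6.2.5.1). PPS2 is defined as "All subjects in PPS1, but excluding those who attended study visits outside of the following windows" (section 6.2.5.2), so it carries the same restriction.

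**Handling of low values.** Section 6.1.1 sets every result below LQ to the single value LQ/2. Section 3 excludes "Previous vaccination with any HBV vaccine". The SAP gives neither the value of LQ nor a numeric definition of seronegative.

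**Other baseline data.** Section 6.2.7 says "The following key sub-groups of interest will be pre-specified" and lists, among others, gender, BMI and smoking status. Height and weight are taken at screening (section 6.1), and age is an entry criterion (section 3).

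**Reuse of the model.** Section 6.3.13.4 applies the same approach to the exploratory GMC ratios. The FAS sensitivity analyses also use it, with and without baseline seropositives.

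**The concern.** The rule for entering the per-protocol sets and the choice of covariate work against each other. A covariate narrows a confidence interval only if it varies among the subjects analyzed and is related to the outcome. In PPS1 and PPS2 the entry rule removes the subjects with high baseline titers, and the LQ/2 rule collapses the rest of the lower range to one point. GMCs reported as adjusted may then be adjusted in name only.

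Precision is what is at stake. All three pairwise 95% CIs must lie within [0.67, 1.5], and enrollment closed early at about 700 per lot instead of 800.

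**Working it through.** **Inputs from the SAP.** SD 0.9 on the log10 scale (an upper bound), margin ±0.176, 95% two-sided CIs, 800 per lot planned and about 700 after early closure (section 4). Section 4 also assumes 10% non-evaluable subjects, stated for the non-inferiority test. Applied here as an assumption, that gives 0.9 × 700 = 630 per lot.

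**Assumptions.** True GMC ratios of 1 (the SAP states none), and R² for the added baseline variables of 0 to 15% (the SAP gives none).

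**Step 1: the plan's own power.** For one pair, power = 2Φ(0.176/SE − 1.96) − 1, with SE = SD × √(2/n).
- n = 800: SE = 0.9 × √(2/800) = 0.0450. 0.176/0.0450 − 1.96 = 1.95, so power is 94.9%.
- n = 700: SE = 0.0481. 0.176/0.0481 − 1.96 = 1.70, so power is 91.1%.

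The planned figure of at least 90% for each pairwise difference is reproduced, with no covariate in the calculation. For all three pairs jointly, simulating three lot means (1,000,000 draws) gives 87.6% at 800 and 79.4% at 700. The latter is close to the plan's figure of more than 80%.

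**Step 2: what the baseline titer can explain in PPS1 and PPS2.** R² = (slope × SD of covariate / 0.9)².
- If seronegative means below LQ, every subject has the value log10(LQ/2). The SD is 0 and R² = 0. The term is collinear with the intercept, and the lot differences and their standard errors are those of a one-way ANOVA.
- If seronegative means below 10 mIU/mL, only values between LQ and 10 vary. Assume LQ of 2 to 5, 1 to 10% of seronegatives quantifiable (spread evenly on the log scale), and slopes of 0.5 to 1. The SD is then 0.05 to 0.21 and R² is 0.0006 to 0.05. A middle case, with LQ 5, 5% quantifiable and slope 1, gives (0.100/0.9)² = 0.012.
- For contrast, in an FAS with an assumed 2 to 5% baseline seropositives (same LQ 5 and 5% quantifiable), R² is 0.02 to 0.18. That is where this covariate can do real work.

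**Step 3: what other baseline variables could add.** Residual SD = 0.9 × √(1 − R²). CI half-width at 700 per lot = 1.96 × residual SD × √(2/700).

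| Assumed R² | Residual SD | Half-width | Reduction, 1 − √(1 − R²) | Joint power, 700 per lot | Joint power, 630 per lot |
|---|---|---|---|---|---|
| 0 | 0.900 | 0.0943 | 0 | 79.4% | 71.4% |
| 5% | 0.877 | 0.0919 | 2.5% | 82.8% | 75.5% |
| 10% | 0.854 | 0.0894 | 5.1% | 86.0% | 79.4% |
| 15% | 0.830 | 0.0869 | 7.8% | 88.9% | 83.3% |

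These figures describe one analysis set. The SAP accepts success in either PPS1 or PPS2, which would raise the pass probability somewhat; the documents do not allow that to be quantified.

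**The case against.** The strongest reply is that nothing in the plan is broken. Lots are assigned at random, so an inert covariate causes no bias and costs at most one degree of freedom among roughly 2,100 subjects. The sample size rests on an SD of 0.9 with no reduction for a covariate, so the planned analysis delivers the precision it was sized for. All of this stands. A reader might infer that the primary comparison is invalid, or that the trial is underpowered because the covariate fails. The documents support neither inference.

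A second reply concerns the alternatives. A reader might take section 6.2.7 as saying that sex, BMI and smoking predict response and are then ignored. It lists them only as sub-groups of interest, and section 1.3 makes the sub-group results exploratory. Age is not on the list. These variables are absent from the primary model but, age apart, are not unused. This also stands, and it is why the R² range is an assumption and not an estimate.

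Third, without LQ or a cut-off, near-absence of variation is an inference. Section 6.1.1 shows that results from 5.0 mIU/mL are handled as numbers, so some quantified values could remain below a 10 mIU/mL cut-off. At the favorable end, the baseline titer reaches an R² of about 0.05, the low end of what is assumed for the added variables. That is a good reason not to remove it.

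Finally, 0.9 is an upper bound for the SD. At an SD of 0.805, joint power at 700 per lot is already 91.6% without covariates, so precision need not turn out to be the limiting factor.

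**Conclusion.** The point holds as a missed gain in precision. It is not an error that threatens the primary conclusion. In PPS1 and PPS2 the only covariate probably explains between nothing and about 5% of outcome variance, and exactly nothing if seronegative means below LQ. The comparison remains valid and unbiased, and the stated power is unaffected.

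The possible gain depends on an R² that the SAP does not give. Over an assumed 5 to 15%, it is a modest narrowing of the intervals and some 3 to 10 percentage points of joint power at 700 per lot. That is worth having when joint power sits near 80% at the planning SD. At R² = 0 nothing is gained and essentially nothing is lost. The conclusion that the baseline titer should be replaced does not follow, because it is informative where seropositives are kept and may be slightly informative elsewhere.

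**What to change.** Before unblinding, amend section 6.3.13.2, and section 6.3.13.4 for the GMC ratios:

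1. Add age (continuous), sex, BMI (continuous) and smoking status to the ANCOVA. Use the same model for PPS1, PPS2 and FAS so that primary and sensitivity results stay comparable.
2. Keep log baseline titer in the model where it varies, and note that it may drop out in PPS1 and PPS2.
3. State LQ and the numeric definition of seronegative, so that the reader can see whether the covariate is constant.
4. Pre-specify a simple rule for missing covariates.

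The cost is SAP wording, one MODEL statement, a few degrees of freedom and the missing-covariate rule. No new data are needed.
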